#### 1.4 Preliminary Data

There is no preliminary data; this is a new study. This interventional phase of this study will be used to generate data on the feasibility and effect sizes of the interventions that will be used for future projects.

#### 1.5 Sample Size Justification

A sample of 80 participants will be enrolled in the cross sectional phase and 40 participants (those with DSP) will continue on to the interventional phase.

The target sample size of 72 (36 with DSP and 36 without DSP) for the cross sectional phase is adequate to explore of between group differences in gait, physical performance, physical activity, and pain pressure threshold variables. For the interventional phase, 36 participants (12 participants in each of the 3 groups) is adequate to demonstrate feasibility and determine effect sizes that can inform a future randomized controlled trial. The expected accrual rate is 90% (drop-out rate of <10%); thus, the number enrolled will be 80.

#### 1.6 Study Variables

##### A. Independent Variables, Interventions, or Predictor Variables

For the cross-sectional phase of the study, gait, physical performance, physical activity, pain severity, pain interference, and pain pressure threshold will be compared between those that have painful distal sensory polyneuropathy and those who do not. See 1.6 B. for a detailed list of variables.

The interventional phase will include 3 treatment groups: transcutaneous nerve stimulation (TENS), mindfulness meditation (MM), and a standard care group (SC). TENS and MM will involve commonly used standards and are not experimental.

**TENS:** TENS settings (frequency, pulse width, and mode) will be set by the investigator prior to giving the unit to the participants. Participants in the TENS group will receive a new battery-operated hand-held TENS300 device (TENSpros.com, St. Louis, MO), 6 sets of electrodes

(TENSpros.com, St. Louis, MO), six 9-volt batteries, and an instruction manual. After the 5th day of baseline physical activity monitoring, they will be provided with a link to a 10-minute instructional video. A dual channel setup will be utilized to deliver one channel to each lower extremity at sites proximal to the feet that have been determined to have protective sensation with at 5.07 gauge (10 gram) Semmes-Weinstein monofilament. Standard settings for chronic pain will be used. Patients will be instructed in how to apply 2"X2" self-adhering electrodes to the designated points on the lower extremities, how to control the intensity, and how to change the battery if needed. They will be advised to self-administer TENS once a day for 30 minutes. Instructions provided to participants will include that they should adjust the intensity of the TENS at the start of the session and again after 15 minutes, as follows: "Turn the intensity dial up to the point where the electrical stimulation feeling is unpleasant or painful, then immediately turn it down just slightly to just below that" and, "after 15 minutes, turn up the intensity dial more to point where is it unpleasant or painful, then turn it down just slightly below that". If participants lose or damage their TENS unit, it will promptly be replaced with a new unit.

**Mindfulness Meditation (MM):** After the 5th day of baseline physical activity monitoring, participants in the MM group will sent a link to view a 10-minute orientation video.. Participants in the MM group will be instructed to complete a 15-30-minute meditation every day. The meditations will be guided by pre-recorded audios, with a different theme each week. Participants will receive a link to the pre-recorded audios by text message and/or email.

**Standard care group:** Participants in the standard care group will be advised to continue with their current pain management strategies and continue to see any health care providers that they normally see. Following 5 days of activity tracing (after their return for data collection at W7), TENS and MM will be offered to them at no cost. If they accept the offer of TENS, they will receive the same equipment and instruction that was provided to those in the TENS group. If they accept the offer of MM, they will be provided with links to the orientation video and the meditation audio recordings.

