## B. Dependent Variables or Outcome Measures

	Type of Variable	Measurement Instrument
Cross-sectional phase Week 0 (all participants)	Temporal and spatial characteristics of gait (walking velocity; step length; step time; stride width; cadence; footfall area)	Zeno instrumented walkway with PKMAS gait analysis software (Protokinetics Inc., Havertown, PA)
	Walking endurance	6-Minute Walk Test
	Physical performance	Short Physical Performance Battery
	Whole body strength	Mid-thigh Pull test
	Pain pressure threshold	Digital Algometer (JTech Medical, Midvale, UT)
	Physical activity over 5 days	Actigraph wGT3X-BT device (Actigraph, Pensacola, FL)
	Physical activity past week	International Physical Activity Questionnaire Short-Form (IPAQ-SF)
	Pain severity Pain interference	Brief Pain Inventory
Interventional phase Week 0 (only those participants)	Quality of life	Medical Outcomes Study HIV Health Survey (MOS-HIV)

with DSP-related pain) Note: variables measured for cross-sectional phase will also be used as outcomes for interventional phase	Depression and/or Anxiety	Hospital Anxiety and Depression Scale (HADS)
	Catastrophizing behaviors	Pain Catastrophizing Scale
	Resilience	6-item Brief Resilience Scale
	Self-reported use of pain medication	Pain management questionnaire
Interventional phase Weeks 1-6 (only those participants with DSP-related pain)	Adherence to home-intervention protocol (fidelity)	Participant responses to daily text messages
Interventional phase Week 7 (only those participants with DSP-related pain)	All variables as listed for Week 0 (including those used in cross-sectional phase)	As listed for Week 0 (including those used in cross-sectional phase)
	Satisfaction (Week 7 only)	Post-intervention Satisfaction Questionnaire
Interventional phase Week 15 (only for those participants with DSP-related pain who were randomized to the TENS or MM groups)	Ongoing use of interventions	Follow up Questionnaire

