Digital Algometer	The blunt tip of the algometer is placed along the dorsal web-space (between 1 st and 2 nd toes) or the proximal	Vaughan, B., McLaughlin, P., & Gosling, C. (2007). Validity of an electronic pressure algometer. International Journal of Osteopathic Medicine , 10(1), 24-28.

	lateral tibia just below the lateral tibial plateau. Pressure is slowly increased until subject reports it is painful, after which the pressure is removed. The value (threshold) is recorded.	Vaughan, B., McLaughlin, P., & Gosling, C. (2007). Validity of an electronic pressure algometer. International Journal of Osteopathic Medicine , 10(1), 24-28.
Brief Pain Inventory	Questionnaire, subscale scores for Pain Intensity and Pain Interference calculated based on responses to questions.	Cleeland, C. S., & Ryan, K. M. (1994). Pain assessment: Global use of the Brief Pain Inventory. Annals Academy of Medicine, Singapore , 23(2):129-138. Keller, S., Bann, C. M., Dodd, S. L., Schein, J., Mendoza, T. R., & Cleeland, C. S. (2004). Validity of the brief pain inventory for use in documenting the outcomes of patients with noncancer pain. The Clinical Journal of Pain , 20(5), 309-318.
Medical Outcomes Study HIV Health Survey (MOS-HIV)	Questionnaire, subscale scores for Physical Quality of Life and Mental Quality of Life are calculated based on responses to questions.	Wu AW, Revicki DA, Jacobson D, Malitz FE. (1997). Evidence for reliability, validity and usefulness of the Medical Outcomes Study HIV Health Survey (MOS-HIV). Qual Life Res , 6(6):481-493.
Hospital Anxiety and Depression Scale (HADS)	Questionnaire, subscale scores for depression or anxiety calculated based on responses to questions.	Bjelland, I., Dahl, A. A., Haug, T. T., & Neckelmann, D. (2002). The validity of the Hospital Anxiety and Depression Scale: an updated literature review. Journal of Psychosomatic Research , 52(2), 69-77. Stern, A. F. (2014). The hospital anxiety and depression scale. Occupational Medicine , 64(5), 393-394.

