#### ▪ Inclusion Criteria

The inclusion criteria for all participants will be:

- diagnosis of HIV infection currently treated with ART
- CD4 count of at least 200 cells/mm^3
- 18-89 years old
- able to read and write in English
- means to travel to a study site.

Half of the sample (those continuing on to the interventional phase) will have painful DSP in the feet. To screen for DSP, potential participants will be asked if they have been diagnosed with DSP in their feet and the Single Question Neuropathy Screen (specifically for symptoms in the feet) will be administered. An affirmative response to either question will be used to classify them as having DSP. For those with DSP, an additional inclusion criteria are:

- average daily self-reported pain in the feet of at least 3/10 on a 0-10 numerical pain scale
- pain in the feet present for at least the past 3 months
- no changes in medications used to manage pain in the past 4 weeks
- availability of a mobile phone to receive text messages over the course of the intervention period
- for interventional phase only: no use of TENS or mindfulness meditation in the prior 6 months

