## 6.0 Data Management Plan

### 6.1 Data Analysis

Cross-sectional phase: We will test for baseline differences between those with painful DSP and those without painful DSP for the set of variables using independent t-tests (or Mann-Whitney tests if distributions are non-normal). Differences between those with and without DSP on potential demographic or clinical confounders will be adjusted for statistically.

Interventional phase: Assuming normality of the outcome variables of interest, between group repeated measures analysis of variance will be used to evaluate differences within and between groups for each outcome separately. In the case of non-normal outcome variable distribution, we will consider transforming the measure to normalize. If normalization is not warranted, then within group changes will be tested using a Friedman's test and between group differences will be compared descriptively. Data will be analyzed using both per-protocol and intention-to-treat analyses in the case of dropouts.

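### The Aim 1 test of Brief Pain Inventory severity is partly circular, because only the DSP group had to report foot pain of at least 3/10 to enter; interference is affected indirectly

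*Combined protocol and SAP*

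**What the plan says.** All references are to the combined protocol and SAP.

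- **Comparison.** Section 1.6 A states that "pain severity, pain interference, and pain pressure threshold will be compared between those that have painful distal sensory polyneuropathy and those who do not". The outcome table in 1.6 B lists "Pain severity Pain interference" (Brief Pain Inventory) among the Week 0 cross-sectional variables for all participants.
- **Test.** Section 6.1: "We will test for baseline differences between those with painful DSP and those without painful DSP for the set of variables using independent t-tests", with Mann-Whitney as the fallback. No variable is exempted. The only adjustment planned is for demographic or clinical confounders.
- **Entry rule.** Section 4.1 C, Inclusion Criteria: "Half of the sample (those continuing on to the interventional phase) will have painful DSP in the feet". For that half the additional criteria include "average daily self-reported pain in the feet of at least 3/10 on a 0-10 numerical pain scale" and "pain in the feet present for at least the past 3 months". Neither the criteria for all participants nor the exclusion table contains a pain floor or ceiling, so the comparison group has no pain criterion.
- **Instrument.** The Study Instruments table in section 1.9 describes the Brief Pain Inventory as "subscale scores for Pain Intensity and Pain Interference calculated based on responses to questions", without restricting it to the feet.
- **Aim 1 itself.** The objective (1.1 A), the hypothesis (1.1 B) and the sample size paragraph (1.5) name gait, physical performance, physical activity and pain pressure threshold; the hypothesis adds walking endurance. None names pain severity or interference.

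**The concern.** One group is admitted through a floor on self-reported pain, the other is not, and self-reported pain is then tested between them. Even if DSP had no bearing on pain, the group with the floor would score higher. A small p-value for severity would therefore partly restate the inclusion criteria.

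The planned adjustment does not help. Demographic and clinical covariates can balance who is in each group, but they cannot undo selection on the outcome. Changing to Mann-Whitney does not help either, because it compares the same selected distributions. Nothing in the plan marks the pain comparison as descriptive or as a check on group definition, so following the text produces a p-value that cannot be interpreted as evidence about DSP.

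**Working it through.** **1. The plan's own figures.** Section 1.5 gives 36 + 36 = 72 completers and less than 10% drop-out. 72/0.9 = 80 and 36/0.9 = 40, so the enrolment numbers reproduce. The plan states no alpha, power, effect size or SD, so there is no power figure to reproduce. For scale, at two-sided 5% and 80% power, 36 per group detects d = (1.96 + 0.84) × √(2/36) = 0.66.

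**2. Inputs.** From the documents: 36 per group, and the floor of 3 on a 0-10 scale in one group only. Assumed, because the documents are silent: SD 2.5, underlying mean 2, 3 or 4 before limiting to 0-10, two-sided 5% level, the same pain distribution in both groups (no true effect), and correlation ρ between the screening score and the tested score.

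**3. Closed form at mean 3, ignoring the 0-10 limits.** Let α = (3 − mean)/SD = 0 and λ = φ(α)/(1 − Φ(α)) = 0.399/0.5 = 0.798.

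- Built-in gap = ρ × SD × λ.
- Variance in the selected group = SD² × [1 − ρ²λ(λ − α)] = 6.25 × (1 − 0.637ρ²).
- d = gap / √(mean of the two variances).
- Rejection ≈ Φ(d√(36/2) − 1.96).

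| ρ | Gap (points) | d | Rejection |
|---|---|---|---|
| 1 | 1.99 | 1.99/2.06 = 0.97 | Φ(4.10 − 1.96) = 98% |
| 0.6 | 1.20 | 1.20/2.35 = 0.51 | Φ(2.16 − 1.96) = 58% |
| 0.3 | 0.60 | 0.60/2.46 = 0.24 | Φ(1.03 − 1.96) = 18% |

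**4. Simulation with scores limited to 0-10** (20,000 studies per cell, t-test, 36 against 36):

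| ρ | Mean 2 | Mean 3 | Mean 4 |
|---|---|---|---|
| 1 | d 1.37, 100% | d 0.97, 98% | d 0.66, 79% |
| 0.6 | d 0.65, 77% | d 0.49, 54% | d 0.35, 31% |
| 0.3 | d 0.31, 26% | d 0.24, 17% | d 0.17, 10% |
| 0 | d 0, 5% | d 0, 5% | d 0, 5% |

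Shorter independent runs agree to within about two percentage points: 79-100% at ρ = 1, 30-77% at 0.6 and 11-24% at 0.3.

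**5. Sensitivity to scoring.** If both scores are whole numbers, a rounded score of 3 admits more people and the bias shrinks: about 58-100% at ρ = 1, 22-63% at 0.6 and 9-19% at 0.3.

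**6. Reading the rows.** Severity is the same kind of measure as the screening score, so the upper rows are the more relevant ones for it. They are diluted to the extent that the inventory captures pain outside the feet. Interference is a different construct and plausibly belongs lower. Which row applies is a judgement that the documents cannot settle.

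**The case against.** **The contrast is painful DSP by design.** Sections 1.1 A, 1.6 A and 6.1 all define the exposure that way, so a null of no effect of DSP on pain is not a hypothesis that the plan states. This stands. It makes the severity test close to a check on group definition, which is a reason to describe severity rather than test it.

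**A reader might infer that the entry rule produces the whole pain difference.** The documents do not support that. The rule screens foot pain, the inventory as described is not confined to the feet, and comparison participants need not be pain-free: section 1.2 cites chronic pain in 39-85% of people with HIV. A real difference may exist as well. What is certain is a built-in component of unknown size.

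**A reader might treat interference like severity and expect a near-certain p-value.** No criterion uses interference, and at correlation 0.3 the rejection rate is about 11-24%. That is above 5% but far from certain. Interference by group is also a fair descriptive question.

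**A reader might infer that pain could carry the Aim 1 conclusion if function shows nothing.** No passage says so, and the objective, hypothesis and sample size paragraph omit both pain scores.

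**The model is not the trial.** Mean, SD and correlation are assumed. The comparison group is also selected to some degree, since anyone affirming a DSP diagnosis or the neuropathy screen is classed as DSP. That may widen the built-in gap, so it does not rescue the test.

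**Conclusion.** The point holds for severity and, in weaker form, for interference. The severity test is partly circular: the inclusion rule contributes a share of any difference, and neither the planned test nor confounder adjustment can separate that share from an effect of DSP. Interference is inflated only as far as it correlates with screened foot pain.

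Under the stated assumptions and no true effect, a nominal 5% test of severity rejects in about 79-100% of studies if severity equals the screening score (58-100% with whole-number scores) and in about 30-77% at correlation 0.6. These figures illustrate the mechanism and are not estimates for this trial.

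The consequence is limited. These are two extra variables in an exploratory cross-sectional phase. The outcomes named in the Aim 1 hypothesis are not themselves entry criteria, and the randomised Aim 2 comparison is unaffected. The change is still worth making, because the severity test as planned is uninformative and the remedy is only wording.

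**What to change.** In sections 1.6 A and 6.1, with the table in 1.6 B aligned:

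- Report Brief Pain Inventory severity by group as a description of the sample, with no between-group test.
- Report interference by group with an estimated difference and confidence interval. State that selection on foot pain inflates the difference and that it is not evidence of an effect of DSP.
- Keep both as Aim 2 outcomes, where all three arms meet the same entry rule and allocation is random.

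Suggested sentence for 6.1: Because the DSP group is selected on foot pain, Brief Pain Inventory severity will be summarised by group without a hypothesis test; interference will be reported with a confidence interval and interpreted in light of that selection.

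The cost is one fewer p-value, for a variable that the Aim 1 hypothesis does not name. Data collection, entry criteria, the named Aim 1 outcomes and the sample size stay as they are.

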## B. Dependent Variables or Outcome Measures

	Type of Variable	Measurement Instrument
Cross-sectional phase Week 0 (all participants)	Temporal and spatial characteristics of gait (walking velocity; step length; step time; stride width; cadence; footfall area)	Zeno instrumented walkway with PKMAS gait analysis software (Protokinetics Inc., Havertown, PA)
	Walking endurance	6-Minute Walk Test
	Physical performance	Short Physical Performance Battery
	Whole body strength	Mid-thigh Pull test
	Pain pressure threshold	Digital Algometer (JTech Medical, Midvale, UT)
	Physical activity over 5 days	Actigraph wGT3X-BT device (Actigraph, Pensacola, FL)
	Physical activity past week	International Physical Activity Questionnaire Short-Form (IPAQ-SF)
	Pain severity Pain interference	Brief Pain Inventory
Interventional phase Week 0 (only those participants)	Quality of life	Medical Outcomes Study HIV Health Survey (MOS-HIV)

with DSP-related pain) Note: variables measured for cross-sectional phase will also be used as outcomes for interventional phase	Depression and/or Anxiety	Hospital Anxiety and Depression Scale (HADS)
	Catastrophizing behaviors	Pain Catastrophizing Scale
	Resilience	6-item Brief Resilience Scale
	Self-reported use of pain medication	Pain management questionnaire
Interventional phase Weeks 1-6 (only those participants with DSP-related pain)	Adherence to home-intervention protocol (fidelity)	Participant responses to daily text messages
Interventional phase Week 7 (only those participants with DSP-related pain)	All variables as listed for Week 0 (including those used in cross-sectional phase)	As listed for Week 0 (including those used in cross-sectional phase)
	Satisfaction (Week 7 only)	Post-intervention Satisfaction Questionnaire
Interventional phase Week 15 (only for those participants with DSP-related pain who were randomized to the TENS or MM groups)	Ongoing use of interventions	Follow up Questionnaire

#### 1.7 Drugs/Devices/Biologics: Not applicable

A. Drug/Device Accountability and Storage Methods: Not applicable

#### 1.8 Specimen Collection

A. Primary Specimen Collection: Not applicable

B. Secondary Specimen Collection: Not applicable

###### ▪ Process of Data Collection:

Data	How it will be collected	Who will oversee the process
Demographic and health information	Questionnaire (web-based using RedCap) Completed on-site	[name] [name] [name]  [name]
Zeno instrumented walkway with PKMAS gait analysis	On-site using portable equipment (Zeno	[name] [name]

software (Protokinetics Inc., Havertown, PA)	instrumented walkway) and laptop computer.	[name] [name]
6-Minute Walk Test	On-site using space in the lab or hallway that is clear.	[name] [name] [name]  [name]
Actigraph GT3X-BT device with ActiLife software (Actigraph, Pensacola, FL)	While on-site, participant will receive instruction in use of Actigraph device. After the participant receives instruction in use of the device, they will be wear it for 5 days, then ship it back to the PI in a pre-paid shipping box.  Data from the participant will be downloaded into a laptop computer before the device is wiped of date, disinfected, and prepared to use with a different participant.	[name]
International Physical Activity Questionnaire Short-Form (IPAQ-SF)	Questionnaire (web-based using RedCap) Completed on-site	[name] [name]  [name]  [name]
Short Physical Performance Battery	On-site, using portable equipment (chair, stopwatch)	[name] [name] [name]  [name]
Mid-thigh Pull	On-site, using portable equipment (load cell platform)	[name] [name] [name]  [name]
Digital Algometer (JTech Medical, Midvale, UT)	On-site, using portable digital algometer	[name] [name] [name]  [name]
Brief Pain Inventory	Questionnaire	[name]

	(web-based using RedCap) Completed on-site	[name] [name] [name]
Medical Outcomes Study HIV Health Survey (MOS-HIV)	Questionnaire (web-based using RedCap) Completed on-site	[name] [name] [name] [name]
Hospital Depression and Anxiety Scale (HADS)	Questionnaire (web-based using RedCap) Completed on-site	[name] [name] [name] [name]
Pain Catastrophizing Scale	Questionnaire (web-based using RedCap) Completed on-site	[name] [name] [name] [name]
Pain management questionnaire	Questionnaire (web-based using RedCap) Completed on-site	[name] [name] [name] [name]
Brief Resilience Scale	Questionnaire (web-based using RedCap) Completed on-site	[name] [name] [name] [name]
Tracking of adherence to home-based treatment	Participant responses to daily text message from a study-specific Twilio account.	[name] [name]
Satisfaction questionnaire	Questionnaire (web-based using RedCap) Completed on-site	[name] [name] [name] [name]
Follow up questionnaire (for those who were in TENS and MM groups)	Questionnaire (web-based using RedCap) Completed at participant's home or location of their choice.	[name]

- **Timing and Frequency:**

Cross-sectional phase: All participants will be seen individually at Week 0 (baseline) for all variables included in the cross-sectional study. In addition, participants will wear an activity monitor for 5 days following the baseline session.

Interventional phase. Participants who continue on into the interventional phase (those with DSP) will complete additional questionnaires at Week 0 and then will be seen again at Week 7 (following 6 weeks of home-based intervention or usual care). In addition, participants will wear an activity monitor for 5 days following the Week 7 session.

At Week 0, the expected time to complete all data collection for those participants without DSP is 45 minutes (gait and physical performance tests) and the expected time for those participants with DSP is 1.5 hours (45 minutes for gait and physical performance tests and 45 minutes for questionnaires.)

At Week 7, the expected time to complete all data collection is 1.5 hours (45 minutes for gait and physical performance tests and 45 minutes for questionnaires.)

At week 15, participants who were randomized to the TENS and MM groups will receive a short follow-up questionnaire (5-10 minutes to complete)

- **Procedures for Audio/Visual Recording:** Not applicable.

- **Study Instruments:**

Instrument	Details	References to support Validity and Reliability
Zeno instrumented walkway	Instrumented walkways are widely used to collect gait data. The walkway is a 15' flat mat placed on the floor. The mat is placed along the loop used for the 6-minute walk test (described below). Data from the 3 laps during the 6-minute walk test will be used. Participants are instructed to walk at their natural pace.	Vallabhajosula, et al. (2019). Concurrent validity of the Zeno walkway for measuring spatiotemporal gait parameters in older adults. Journal of Geriatric Physical Therapy , 42(3), E42-E50. Lynall, R. C., Zukowski, L. A., Plummer, P., & Mihalik, J. P. (2017). Reliability and validity of the protokinetics movement analysis software in measuring center of pressure during walking. Gait & Posture , 52, 308-311.
6-Minute Walk Test	A 60' loop is marked on the floor with traffic cones. Participants are instructed to walk at their natural pace. Over 6 minutes of walking, the number of completed laps are counted. A rolling measurement wheel is used to measure the distance walked during the final lap (if not full) at 6 minutes.	ATS statement: guidelines for the six-minute walk test. (2002). ATS committee on proficiency standards for clinical pulmonary function laboratories. Am J Respir Crit Care Med , 166(1), 111-117. Perera, S., Mody, S. H., Woodman, R. C., & Studenski, S. A. (2006). Meaningful change and responsiveness in common physical performance measures in older adults. Journal of the American Geriatrics Society , 54(5), 743-749..

Actigraph wGT3X-BT device	The Actigraph device resembles a watch. It is worn around the wrist. It should be worn continuously during the prescribed 5-day period except for when it is removed for re-charging.	Acebo, C., & LeBourgeois, M. K. (2006). Actigraphy. Respiratory Care Clinics of North America , 12(1), 23-30. Aadland, E., & Ylvisåker, E. (2015). Reliability of the Actigraph GT3X+ accelerometer in adults under free-living conditions. PLoS One , 10(8), e0134606.
International Physical Activity Questionnaire Short-Form (IPAQ-SF)	Questionnaire, self-report estimate of physical activity over past 7 days	Lee, P. H., Macfarlane, D. J., Lam, T. H., & Stewart, S. M. (2011). Validity of the international physical activity questionnaire short form (IPAQ-SF): A systematic review. International journal of behavioral nutrition and physical activity , 8(1), 1-11. Craig, C., Marshall, A., Sjostrom, M., Bauman, A., Lee, P., Macfarlane, D., ... & Stewart, S. (2017). International physical activity questionnaire-short form. J Am Coll Health , 65(7), 492-501.
Short Physical Performance Battery (SPPB)	The SPPB includes 3 tests: Balance tests that involved timed standing (up to 10 sec. each) in side-by-side standing, semi-tandem standing and tandem standing.  Gait speed over a 4-meter distance is calculated.  Timed 5 time-sit-to-stand test. The participant rises from sitting a chair 5 times.	Mijnarends, D. M., Meijers, J. M., Halfens, R. J., ter Borg, S., Luiking, Y. C., Verlaan, S., ... & Schols, J. M. (2013). Validity and reliability of tools to measure muscle mass, strength, and physical performance in community-dwelling older people: a systematic review. Journal of the American Medical Directors Association , 14(3), 170-178. Westman, A. W., Combs-Miller, S., Moore, J., & Ehrlich-Jones, L. (2019). Measurement characteristics and clinical utility of the short physical performance battery among community-dwelling older adults. Archives of Physical Medicine and Rehabilitation , 100(1), 185-187.
Mid-thigh Pull	The participant stands on a testing platform with hips and knees slightly bent, and holds a handle bar that is connected to the platform via a chain and linked to a force gauge. The participant is instructed to pull up on the bar with maximum effort for 5 seconds. This is repeated 3 times and the maximum value is recorded. The test serves as an indicator of total body strength.	Comfort, P., Dos' Santos, T., Beckham, G. K., Stone, M. H., Guppy, S. N., & Haff, G. G. (2019). Standardization and methodological considerations for the isometric midthigh pull. Strength & Conditioning Journal , 41(2), 57-79. Brady, C. J., Harrison, A. J., & Comyns, T. M. (2018). A review of the reliability of biomechanical variables produced during the isometric mid-thigh pull and isometric squat and the reporting of normative data. Sports Biomechanics , 19(1), 1-25.
Digital Algometer	The blunt tip of the algometer is placed along the dorsal web-space (between 1 st and 2 nd toes) or the proximal	Vaughan, B., McLaughlin, P., & Gosling, C. (2007). Validity of an electronic pressure algometer. International Journal of Osteopathic Medicine , 10(1), 24-28.

	lateral tibia just below the lateral tibial plateau. Pressure is slowly increased until subject reports it is painful, after which the pressure is removed. The value (threshold) is recorded.	Vaughan, B., McLaughlin, P., & Gosling, C. (2007). Validity of an electronic pressure algometer. International Journal of Osteopathic Medicine , 10(1), 24-28.
Brief Pain Inventory	Questionnaire, subscale scores for Pain Intensity and Pain Interference calculated based on responses to questions.	Cleeland, C. S., & Ryan, K. M. (1994). Pain assessment: Global use of the Brief Pain Inventory. Annals Academy of Medicine, Singapore , 23(2):129-138. Keller, S., Bann, C. M., Dodd, S. L., Schein, J., Mendoza, T. R., & Cleeland, C. S. (2004). Validity of the brief pain inventory for use in documenting the outcomes of patients with noncancer pain. The Clinical Journal of Pain , 20(5), 309-318.
Medical Outcomes Study HIV Health Survey (MOS-HIV)	Questionnaire, subscale scores for Physical Quality of Life and Mental Quality of Life are calculated based on responses to questions.	Wu AW, Revicki DA, Jacobson D, Malitz FE. (1997). Evidence for reliability, validity and usefulness of the Medical Outcomes Study HIV Health Survey (MOS-HIV). Qual Life Res , 6(6):481-493.
Hospital Anxiety and Depression Scale (HADS)	Questionnaire, subscale scores for depression or anxiety calculated based on responses to questions.	Bjelland, I., Dahl, A. A., Haug, T. T., & Neckelmann, D. (2002). The validity of the Hospital Anxiety and Depression Scale: an updated literature review. Journal of Psychosomatic Research , 52(2), 69-77. Stern, A. F. (2014). The hospital anxiety and depression scale. Occupational Medicine , 64(5), 393-394.
Pain Catastrophizing Scale	Questionnaire, overall score calculated based on responses to questions.	Osman, A., Barrios, F. X., Gutierrez, P. M., Kopper, B. A., Merrifield, T., & Grittman, L. (2000). The Pain Catastrophizing Scale: Further psychometric evaluation with adult samples. Journal of Behavioral Medicine , 23(4), 351-365. Osman, A., Barrios, F. X., Kopper, B. A., Hauptmann, W., Jones, J., & O'Neill, E. (1997). Factor structure, reliability, and validity of the Pain Catastrophizing Scale. Journal of Behavioral Medicine , 20(6), 589-605.
Brief Resilience Scale	Questionnaire, overall score calculated based on responses to questions	Kyriazos, T. A., Stalikas, A., Prassa, K., Galanakis, M., Yotsidi, V., & Lakioti, A. (2018). Psychometric evidence of the Brief Resilience Scale (BRS) and modeling distinctiveness of resilience from depression and stress. Psychology , 9(7), 1828-1857.

Pain management questionnaire	Questionnaire	No reliability or validity to report; questions are custom designed for this study.
Tracking of adherence to treatment	Daily question via text message	No reliability or validity to report; question is custom designed for this study.
Post-intervention Satisfaction Questionnaire	Questionnaire	No reliability or validity to report; questions are custom designed for this study.
Follow up questionnaire	Questionnaire	No reliability or validity to report; questions are custom designed for this study.

- **Ethnographic Studies, Interviews, Or Observation:** Not applicable.
- **Subject Identifiers:** No subject identifiers outside of the participant identification number will be linked to the data.

